**6.1.2.7 Tumor Tissue Collection and Correlative Studies Blood Sampling**

Tissue and tumor collection will be performed at diagnosis and at surgical resection or rebiopsy, as described in Section 4.2.3 above.

**6.1.3 Laboratory Procedures/Assessments**

Details regarding specific laboratory procedures/assessments to be performed in this trial are provided below.

Laboratory tests for hematology, chemistry, urinalysis, and others are specified in Table 5.

Table 5 Laboratory Tests

Hematology	Chemistry	Urinalysis	Other
Hematocrit	Albumin	Blood	Serum $\beta$ -human chorionic gonadotropin†
Hemoglobin	Alkaline phosphatase	Glucose	( $\beta$ -hCG)†
Platelet count	Alanine aminotransferase (ALT)	Protein	PT (INR)
WBC (total and differential)	Aspartate aminotransferase (AST)	Specific gravity	aPTT
Red Blood Cell Count	Lactate dehydrogenase (LDH)	Microscopic exam ( If abnormal )	Total triiodothyronine (T3)
Absolute Neutrophil Count	Carbon Dioxide ‡	results are noted	Free thyroxine (T4)
Absolute Lymphocyte Count	( $CO_2$ or bicarbonate)	Urine pregnancy test †	Thyroid stimulating hormone (TSH)
	Uric Acid		
	Calcium		
	Chloride		Blood for correlative studies
	Glucose		
	Phosphorus		
	Potassium		
	Sodium		
	Magnesium		
	Total Bilirubin		
	Direct Bilirubin ( If total bilirubin is elevated above the upper limit of normal )		
	Total protein		
	Blood Urea Nitrogen		

† Perform on women of childbearing potential only. If urine pregnancy results cannot be confirmed as negative, a serum pregnancy test will be required.

‡ If considered standard of care in your region.

Laboratory tests for screening or entry into the Second Course Phase should be performed within 45 days prior to the first dose of treatment. All screening studies should be done within 45 days of radiation therapy. The exception to this guideline is laboratory tests, which should be done within 15 days of radiation therapy. After Cycle 1, pre-dose laboratory procedures can be conducted up to 72 hours prior to dosing. Results must be reviewed by the investigator or qualified designee and found to be acceptable prior to each dose of trial treatment.

### **6.1.3.1 Pharmacokinetic/Pharmacodynamic Evaluations**

#### **6.1.3.1.1 Blood Collection for Serum Pembrolizumab**

Sample collection, storage and shipment instructions for serum samples will be provided in the Laboratory Manual.

#### **6.1.3.1.2 Blood Collection for Anti-Pembrolizumab Antibodies**

Sample collection, storage and shipment instructions for blood samples will be provided in the Laboratory Manual.

### **6.1.4 Other Procedures**

#### **6.1.4.1 Withdrawal/Discontinuation**

**Off-Study Criteria.** Patients will remain on study until completion until they: 1) experience a Grade 3 or higher toxicity during radiation therapy (in which case they will be deemed to be non-evaluable), 2) meet the criteria of Permanent Discontinuation/Off-Study Criteria outlined in Table 3 above (evaluable patient), in which case subjects will be followed until **resolution of symptoms**, 3) are lost-to follow-up, 4) elect to come off study, or 5) die.

When a subject discontinues/withdraws prior to trial completion, all applicable activities scheduled for the final trial visit should be performed at the time of discontinuation. Any adverse events which are present at the time of discontinuation/withdrawal should be followed in accordance with the safety requirements outlined in Section 7.2 - Assessing and Recording Adverse Events. Subjects who a) attain a CR or b) complete 24 months of treatment with pembrolizumab may discontinue treatment with the option of restarting treatment if they meet the criteria specified in Section 7.1.5.5. After discontinuing treatment following assessment of CR, these subjects should return to the site for a Safety Follow-up Visit (described in Section 7.1.5.3.1) and then proceed to the Follow-Up Period of the study (described in Section 7.1.5.4).

If a patient comes off study for toxicity, follow-up will still occur through the research team +/- clinical staff for survival purposes, either through clinic visits as clinically warranted or direct patient calls if the patient no longer follows up at our institution.

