#### **4.2.3 Rationale for Endpoints**

Given the lack of experience combining radiation therapy for MPM and immunotherapy, the primary endpoint will be high-grade toxicity, defined specifically in Table 3 below. Specifically, the Off-Study Criteria defined in Table 3 are the “Unacceptable” high-grade toxicities in the trial. That is, patients that meet these criteria will be considered as having met the study endpoint and will be taken off study. Patients will be monitored for 4 months after the start of RT. Since RT is approximately 1 month in duration, this monitoring period will include 3 months after the end of RT.

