#### 4.4.1.2 Dose Modification

Adverse events (both non-serious and serious) associated with pembrolizumab exposure may represent an immunologic etiology. These adverse events may occur shortly after the first dose or several months after the last dose of treatment. Pembrolizumab must be withheld for drug-related toxicities and severe or life-threatening AEs as per Table 3 below. See Section 5.6.1 and Events of Clinical Interest Guidance Document for supportive care guidelines, including use of corticosteroids.

Table 3

Dose Modification Guidelines for Drug-Related Adverse Events (Note that discontinuation of subjects for all toxicities in Table 3 are contingent on the conclusion that they are treatment related.)

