All Other Drug-Related Toxicity 	3 or Severe	Toxicity resolves to Grade 0-1	Toxicity does not resolve within 12 weeks of last dose or inability to reduce corticosteroid to 10 mg or less of prednisone or equivalent per day within 12 weeks.
	4	Permanently discontinue	Permanently discontinue/Off-Study
All other Radiation-Related Toxicity by CTCAE v4.0 criteria (cardiac, esophageal, pericarditis, bowel, etc)	3 or greater	Off Study	Off Study

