### *Management of Radiation Pneumonitis*

Patients who develop Grade  $\geq 2$  pneumonitis will be managed according to standard clinical guidelines. If supportive measures are unsuccessful, and/or if the symptoms persist despite this approach, steroids and a referral to pulmonary medicine will be considered. A standard regimen of prednisone includes 40-60 mg daily x 2 weeks, then tapering over the next 3-6 weeks based on symptom status. Interventions such as hospitalization, intravenous steroids, and oxygen administration will be performed at the treating physician's discretion.

As noted in the Statistical Considerations section below (Section 8.0), the study will be stopped if 3/6 or 6/12 patients develop Grade 3 or higher radiation pneumonitis. If 0/6, 1/6, or 2/6 patients develop this toxicity, the study will continue. No dose de-escalation will be performed because all patients are already receiving the minimal therapeutic microscopic dose of radiation, and therefore any further reductions in treatment intensity are not likely to control the disease (and still carry the risk of toxicity). Furthermore, our institution does not have experience escalating the radiation dose in mesothelioma higher than that described in this study, and thus it is not appropriate to do so in conjunction with Pembrolizumab without first assessing the effect of higher doses of radiation therapy alone (without immunotherapy). The study is thus addressing the question of whether our institution's current radiation regimen for malignant pleural mesothelioma, in both the unresectable and pleurectomy/decortication settings, is safe with Pembrolizumab. In essence, the two regimens that we are testing are those in the two cohorts that we have included, the first being the most aggressive and including the entire hemithorax (Cohort 1), and the second being a much more limited field and including only the region of palliation (Cohort 2). This trial will provide data as to whether the immunotherapy-radiation combination should be further explored in neither context, only the less aggressive scenario, or in both patient populations.

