### **7.2 Statistical Analysis Plan**

We will enroll a total of 24 patients, twelve patients to each cohort consisting of distinct radiation and immunotherapy treatment plans. For each study cohort, treatment-related toxicity is defined in Table 3 above (in the column “Discontinue Treatment/Off-Study Criteria”. Therefore, any patient meeting this criteria will be deemed to have experienced an “unacceptable” toxicity for the purposes of the trial. For each study condition, we plan to enroll 12 patients in cohorts of size 6. All patients will be monitored for at least 4 months from the beginning of RT, before declaring the treatment acceptable for enrolling the next cohort of 6 patients.

Continuous monitoring using the method of Thall [20] will be employed for each study cohort of 12 patients in cohorts of size 6 where each patient is monitored for at least 4 months from the start of RT. We will stop the trial if we have reason to believe that the treatment-related toxicity rate is more than 30%. Using the following probability rule

$$\Pr(\text{rate of treatment-related toxicity 4 months from the start of RT} > 30\% \mid \text{data}) > 0.80.$$

If we determine there is more than a 80% chance that the treatment-related toxicity rate is more than 30%, we will stop the trial. We will assume a beta(0.6, 1.4) distribution for treatment-related toxicity as this prior provides a mean of 30% and a standard deviation of 26.5%. Thus the trial will be stopped if

$$[\# \text{ of patients with treatment-related toxicity 4 months from day 1 of the start of RT} / \# \text{ of patients evaluated}]$$

$$\geq 3/6, 6/12$$

Therefore, we will stop either study cohort if we observe 3 or more treatment-related toxicities in the first 6 patients, or if we observe 6 treatment related toxicities at any time while evaluating all 12 patients. We will suspend accrual while evaluating the first 6 patients to ensure none of

the stopping boundaries have been reached prior to enrolling the final 6 patients of each study cohort. The operating characteristics from this decision rule are shown in Table X and are based on 1000 simulations for each scenario.

Table X. Operating characteristics for toxicity monitoring rule

Treatment-related Toxicity 4 months after start of RX	Probability of Stopping Early	Sample Size Avg
0.10	0.017	11.9
0.20	0.099	11.4
0.30	0.254	10.5
0.40	0.462	9.2
0.50	0.650	8.1

- Operating Characteristics acquired using the Stata command stopbound

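### A treatment-related Grade 3+ radiation toxicity during RT is a primary-endpoint event under Section 7.2, but Section 6.1.4.1 makes that patient non-evaluable, and one such patient can reverse the stopping decision

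*Combined protocol and SAP*

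**What the plan says.** **Endpoint and window.** Section 4.2.3 makes the off-study column of Table 3 the primary endpoint: "patients that meet these criteria will be considered as having met the study endpoint and will be taken off study". Monitoring lasts four months from the start of RT. RT is taken to last about one month, so "this monitoring period will include 3 months after the end of RT". The RT month is therefore inside the window.

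**Table 3 (Section 4.4.1.2).** The last row covers "All other Radiation-Related Toxicity by CTCAE v4.0 criteria (cardiac, esophageal, pericarditis, bowel, etc". At Grade 3 or above the patient goes off study, with no exemption for events before RT ends. The note above the table limits it by attribution: "discontinuation of subjects for all toxicities in Table 3 are contingent on the conclusion that they are treatment related".

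**Stopping rule.** Section 7.2 adopts the same column. Its numerator is the number "of patients with treatment-related toxicity 4 months from day 1 of the start of RT", its denominator is the patients evaluated, and its boundaries are 3 of 6 and 6 of 12 per cohort.

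**Evaluability.** Section 6.1.4.1 lists the off-study reasons. Item 1 covers patients who "experience a Grade 3 or higher toxicity during radiation therapy (in which case they will be deemed to be non-evaluable". Item 2 covers patients who "meet the criteria of Permanent Discontinuation/Off-Study Criteria outlined in Table 3 above (evaluable patient".

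**Use of the term in Section 7.2.** The section plans 12 enrolled patients per cohort. Its closing paragraph times the medical monitor's summaries by the first six evaluable patients and then the next six. It neither defines evaluable nor mentions replacement.

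**Restatement.** The radiation pneumonitis text in Section 4.4.1.2 refers back to the statistical section and gives the rule in narrower words: "the study will be stopped if 3/6 or 6/12 patients develop Grade 3 or higher radiation pneumonitis".

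**The concern.** Take a patient with Grade 3 esophageal toxicity during RT that is attributed to the radiation. Under Section 7.2 this is an event. Under item 2 of Section 6.1.4.1 the patient is evaluable; under item 1 the patient is not. Both items stand in the same sentence and neither is given priority.

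The choice affects the numerator and the denominator of the primary endpoint, and of the trial's only numerical stopping rule, in cohorts of 12. If it stays open, it will be made after the event is known, in an open-label trial where the principal investigator or a designee also assigns attribution (Section 6.1.2.1).

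**Working it through.** **1. Inputs, all from Section 7.2.** The prior is beta(0.6, 1.4). The rule is to stop if Pr(rate > 0.30 | data) > 0.80. Looks are planned at 6 and 12 patients.

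**2. Reproducing the plan's figures.**
- Prior mean: 0.6/(0.6+1.4) = 0.30. Prior SD: √[0.6×1.4/(2²×3)] = √0.07 = 0.265. Both match.
- With x events in n patients the posterior is beta(0.6+x, 1.4+n−x). The tail above 0.30 is 0.523 at 2/6, 0.800003 at 3/6, 0.772 at 5/12 and 0.905 at 6/12. The boundaries 3/6 and 6/12 follow.
- Table X's stopping column is reproduced by the first look alone, P(X ≥ 3 | n = 6, p):

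| True rate p | Exact | Table X |
|---|---|---|
| 0.10 | 0.016 | 0.017 |
| 0.20 | 0.099 | 0.099 |
| 0.30 | 0.256 | 0.254 |
| 0.40 | 0.456 | 0.462 |
| 0.50 | 0.656 | 0.650 |

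The small differences are in keeping with 1000 simulations per scenario.

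**3. The same patients under each rule.** Suppose one of the observed toxicities is a treatment-related Grade 3+ radiation toxicity during RT. The pattern is constructed, but no toxicity rate is assumed.

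| Look | Counted (Section 7.2, item 2) | Excluded, replaced by a patient without toxicity (item 1) |
|---|---|---|
| First | 3/6, beta(3.6, 4.4): 0.800003, stop | 2/6, beta(2.6, 5.4): 0.523, continue |
| Final | 6/12, beta(6.6, 7.4): 0.905, boundary met | 5/12, beta(5.6, 8.4): 0.772, not met |

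If the replacement at the first look also has a toxicity, the count returns to 3/6 and the cohort stops.

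**4. Direction over many trials.** Item 1 has no attribution limit. It removes treatment-related events, which lowers the count. It also removes patients with unrelated Grade 3+ toxicity during RT, who might otherwise have counted as non-events. The net effect depends on both RT-phase rates. The documents give neither, and the pneumonitis figures in Section 4.1 are not split by whether the event came during RT.

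**The case against.** The best defence is that item 1 is the only rule written for toxicity during RT, so it works as a specific exception to the general Table 3 rule. Several places fit a post-RT endpoint. The objective in Section 3.1 concerns pembrolizumab given after RT. The note to Table 2 in Section 4.4 starts the drug after the last day of RT, so a patient taken off during RT never receives it. Table 3 is titled for drug-related events, Section 6.2 treats pembrolizumab as the intervention, and the end of Section 7.2 speaks of evaluable patients.

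This reading is coherent and may be what was intended, but it is not stated as the rationale. Sections 4.2.3 and 7.2 both start the window on the first day of RT. Section 6.1.5.2 puts RT inside the treatment period, and Section 7.1 says the study assesses the toxicity of two radiation plans. The reference to evaluable patients governs the medical monitor's summary, not the boundary.

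Four stronger readings are tempting, and the documents do not support them.
- *Section 7.2 is silent on what to count.* Read alone, it is clear: the Table 3 column from day 1 of RT. The defect is its conflict with Section 6.1.4.1.
- *The pneumonitis text is a separate safeguard.* It refers back to the statistical section, so it restates that rule and adds no independent one.
- *Table X is wrong.* It is valid for whichever rate is monitored. Only its label, which reads RX where the text has RT, needs clarifying.
- *The plan hides toxicity.* Grade 3+ events during RT are recorded with attribution (Sections 6.1.2.1 and 6.2) and toxicities are tabulated (Section 7.2). What is unsettled is whether they enter the 3/6 and 6/12 counts.

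**Conclusion.** The conflict is real and goes beyond missing detail, because following item 1 can give a different decision from following Section 7.2. One reclassified patient moves the first look from stop to continue. That sensitivity arises partly because 3/6 clears 0.80 by only 0.000003. At the final look accrual is complete, so the change from 6/12 to 5/12 affects the declared conclusion rather than further enrolment.

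The examples assume that one toxicity falls during RT, is judged treatment-related, and is replaced by a patient without toxicity. How often that would happen cannot be worked out from the documents, so the overall size is unknown, and a consistent understatement of toxicity is not established. Confidence is high for the inconsistency in the text and for the single-patient arithmetic, and does not extend to the long-run effect.

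**What to change.** Reconcile Sections 4.2.3, 6.1.4.1 and 7.2, Table 3, and the pneumonitis text that restates the rule. In Section 7.2, define evaluable once, covering unrelated Grade 3+ events during RT, and say whether non-evaluable patients are replaced.

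- **If the endpoint stays as counted from the start of RT:** count treatment-related RT-phase Grade 3+ toxicities as events and keep those patients in the denominators of 6 and 12.
- **If a post-RT endpoint is intended:** change the start-of-RT wording in Sections 4.2.3 and 7.2 and clarify the Table X label.
- **In either case:** report RT-phase Grade 3+ toxicity over all patients who started RT.

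This changes counting only, not when treatment stops or how patients are managed. No new data are needed, because RT-phase Grade 3+ events and their attribution are already collected. The cost of the first option is wording plus one definition; the second is a larger amendment because it changes the endpoint window. On the downside, the reported toxicity rate may look less favourable and a cohort may be more likely to reach the boundary. If non-evaluable patients are replaced, enrolment may exceed 12 per cohort.

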### **6.1.4.2 Blinding/Unblinding**

### **6.1.5 Visit Requirements**

Visit requirements are outlined in Section 6.0 - Trial Flow Chart. Specific procedure-related details are provided above in Section 7.1 - Trial Procedures.

#### **6.1.5.1 Screening**

##### **6.1.5.1.1 Screening Period**

Patients will be screened with the appropriate tests prior to entering the study.

#### **6.1.5.2 Treatment Period**

The treatment period will encompass both the radiation therapy and the Pembrolizumab, administered as described above. Patients will undergo assessment of disease status

#### **6.1.5.3 Post-Treatment Visits**

##### **7.1.5.3.1 Safety Follow-Up Visit**

The mandatory Safety Follow-Up Visit should be conducted approximately 30 days after the last dose of trial treatment or before the initiation of a new anti-cancer treatment, whichever comes first. All AEs that occur prior to the Safety Follow-Up Visit should be recorded. Subjects with an AE of Grade > 1 will be followed until the resolution of the AE to Grade 0-1 or until the beginning of a new anti-neoplastic therapy, whichever occurs first. SAEs that occur within 90 days of the end of treatment or before initiation of a new anti-cancer treatment should also be followed and recorded. Subjects who are eligible for retreatment with pembrolizumab (as described in Section 7.1.5.5) may have up to two safety follow-up visits, one after the Treatment Period and one after the Second Course Phase.

#### **6.1.5.4 Follow-up Visits**

Subjects who discontinue trial treatment for a reason other than disease progression will move into the Follow-Up Phase and should be assessed every 6 weeks ( $42 \pm 7$  days) by radiologic imaging to monitor disease status. After 48 weeks the imaging time point will occur every 12 weeks ( $\pm 7$  days), up to 5 years. Every effort should be made to collect information regarding disease status until the start of new anti-neoplastic therapy, disease progression, death, end of the study or if the subject begins retreatment with pembrolizumab as detailed in Section 7.1.5.5. Information regarding post-study anti-neoplastic treatment will be collected if new treatment is initiated.

Subjects who are eligible to receive retreatment with pembrolizumab according to the criteria in Section 7.1.5.5 will move from the follow-up phase to the Second Course Phase when they experience disease progression. Details are provided in Section 6.2 – Trial Flow Chart for Retreatment.

#### **6.1.5.4.1 Survival Follow-up**

Once a subject experiences confirmed disease progression or starts a new anti-cancer therapy, the subject moves into the survival follow-up phase and should be contacted by telephone every 12 weeks to assess for survival status until death, withdrawal of consent, or the end of the study, whichever occurs first.

#### **6.1.5.5 Second Course Phase (Retreatment Period)**

Subjects who stop pembrolizumab with SD or better may be eligible for up to one year of additional pembrolizumab therapy if they progress within one year after stopping study treatment. This retreatment is termed the Second Course Phase of this study and is only available if the study remains open and the subject meets the following conditions:

- **Either**

- Stopped initial treatment with pembrolizumab after attaining an investigator-determined confirmed CR according to RECIST 1.1, and
  - Was treated for at least 24 weeks with pembrolizumab before discontinuing therapy
  - Received at least two treatments with pembrolizumab beyond the date when the initial CR was declared

**OR**

- Had SD, PR or CR and stopped pembrolizumab treatment after 24 months of study therapy for reasons other than disease progression or intolerance

**AND**

- Experienced an investigator-determined confirmed radiographic disease progression after stopping their initial treatment with pembrolizumab
- Did not receive any anti-cancer treatment since the last dose of pembrolizumab
- Has a performance status of 0 or 1 on the ECOG Performance Scale
- Demonstrates adequate organ function as detailed in Section 5.1.2

- Female subject of childbearing potential should have a negative serum or urine pregnancy test within 72 hours prior to receiving retreatment with study medication.
- Female subject of childbearing potential should be willing to use 2 methods of birth control or be surgically sterile, or abstain from heterosexual activity for the course of the study through 120 days after the last dose of study medication (Reference Section 5.7.2). Subjects of child bearing potential are those who have not been surgically sterilized or have been free from menses for > 1 year.
- Male subject should agree to use an adequate method of contraception starting with the first dose of study therapy through 120 days after the last dose of study therapy.
- Does not have a history or current evidence of any condition, therapy, or laboratory abnormality that might interfere with the subject's participation for the full duration of the trial or is not in the best interest of the subject to participate, in the opinion of the treating investigator.
- Absence of rapid progression of disease
- Absence of progressive tumor at critical anatomical sites (e.g. cord compression) requiring urgent alternative medical intervention.

Subjects who restart treatment will be retreated at the same dose and dose interval as when they last received pembrolizumab. Treatment will be administered for up to one additional year.

Visit requirements are outlined in Section 6.0 – Trial Flow Chart.

